1. INTRODUCTION

1.1. Study Overview

Title	Effects of Recombinant Human Glutamic Acid Decarboxylase (rhGAD65) Formulated in Alum (GAD-alum) on the Progression of Type 1 Diabetes in New Onset Subjects							
IND Sponsor	Type 1 Diabetes Trial Network (TrialNet)							
Conducted By	Type 1 Diabetes Trial Network (TrialNet)							
Protocol Chair	[name]							
Accrual Objective	126 subjects over 2 years							
Study Design	The study is a three-arm, multicenter, randomized, double- masked, placebo-controlled clinical trial. All groups will receive standard intensive diabetes treatment with insulin and dietary management.							
Treatment Description	Recombinant human glutamic acid decarboxylase (rhGAD65), formulated in aluminum hydroxide is an antigen-specific immune modulator that has been shown to slow or prevent autoimmune destruction of pancreatic beta cells by inducing immune "tolerance". Participants will receive 3 injections consisting of 20µg of GAD-Alum x 3, 20µg of GAD-Alum x 2 plus one injection of placebo-Alum, or placebo-Alum x 3.							
Study Duration	Total duration is approximately 4 years (2 years accrual and 2 years follow-up). Follow-up for up to 4 years may continue for those who have persistence of beta cell function after 2 years and/or detectable immunologic effects of treatment by descriptive analysis.							
Objective	It is hypothesized that multiple injections with 20µg GAD-alum preserves endogenous insulin production in type 1-diabetes patients 3-45 years of age, when diagnosed within 3 months prior to the first injection.							
Primary Outcome	The primary statistical hypothesis to be assessed in this study is whether the mean C-peptide value at one year for study subjects receiving three injections with GAD-Alum vaccine differs significantly from the mean value for placebo subjects, or if the mean C-peptide value for study subjects receiving two injections with GAD-Alum vaccine differs significantly from the mean value for placebo subjects.							
Secondary Goals	The study will examine the effect of the proposed treatment on surrogate markers for immunologic effects, namely disease-specific outcomes and immunological outcomes.							
Major Inclusion	Type 1 diabetes within past 3 months							
Criteria	Age 3-45 years**							
	Presence of GAD65 antibody							

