4.9. Post-treatment Follow-up

All subjects treated with injections of 20µg GAD-Alum or Alum alone will be evaluated over a two year period. Subjects may subsequently be asked to undergo additional follow-up for an additional two years with a visit every 6 months until study end. Subjects with undetectable levels of C-peptide on the 30 month visit will not undergo any further MMTTs for assessment of C-peptide levels at subsequent visits.

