6.3. Mechanistic Outcome Assessments

TrialNet will perform immune and genetic assays to further understand mechanisms that may be underlying the Type 1 disease process and response to therapy. For this purpose, samples for PBMC, DNA, RNA, plasma, and serum will be obtained. HLA testing will be done.

The primary mechanistic studies are those which measure GAD65-specific immune responses. The principle objective is to identify measures of immunity to GAD which distinguish between subjects receiving two or three injections of GAD in alum, as compared to those receiving alum injections alone.

Additional objectives are:

(i) To determine whether these measures of GAD immunity reflect immune deviation, changes in GAD epitope recognition or amplification of GAD regulatory function;

(ii) To evaluate other T1D-associated immune responses, such as anti-proinsulin or anti-IA2, as markers for antigen-spreading and bystander effects; and

(iii) To correlate changes in GAD65-specific immune responses with levels of c-peptide over the 24-month duration of the trial.

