9.2. Secondary Outcome and Analyses

Additional analyses of the primary outcome will include:

- a log rank test of the difference in the hazard function between groups in the first occurrence of a loss of the 2 hour peak C-peptide < 0.2 pmol/ml on a semiannual MMTT (48), and
- longitudinal analyses (45) using mixed effects models with a random intercept and slope of the C-peptide values over the post-treatment period, adjusted for the baseline level of C-peptide. The average intercept and slope will be compared between groups adjusting for age, gender and the baseline $log(Y_{Cp} + 1)$.
- Analyses will also be conducted to adjust for baseline $log(Y_{Cp} + 1)$ and HbA1c levels, and by age, gender and race/ethnicity, as appropriate.
- Analyses will also be conducted to examine the effect of HLA or other genotype and immune phenotypes

Additional secondary objectives are to examine how the GAD-Alum vaccine affects the following:

- Mean C-peptide (as previously described) from the stimulated C-peptide curve over both 2 and 4 hours at 24 months for those age 12 or older
- Mean C-peptide (as previously described) from the stimulated C-peptide curve over 2 hours at 18 months
- HbA1c
- Insulin dose (units/kg)
- Blood glucose
- Number and severity of adverse events
- Hypoglycemia
 - Number of major hypoglycemic events (defined as loss of consciousness, seizure, or requiring assistance from another person because of altered state of consciousness)
 - Reported hypoglycemic events confirmed with capillary blood glucose measurement less than 70 mg/dl.
 - For individuals for whom continuous glucose monitoring data is available
 - Area under the curve and number of events less than 70 mg/dl on the continuous glucose monitoring record
 - Hyperglycemia as measured as the area under the curve and number of events greater than 180 mg/dl on the CGMS record prior to each study visit
 - Glycemia and glycemic variability prior to each MMTT visit
 - The daily mean level of glucose, as well as the levels before and after meals will be computed.
 - Measures of diurnal variability in glucose will be measured by the J-value, standard deviation of glucose values, and the mean amplitude of glycemic excursion (MAGE)

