9.4. Sample Size and Power Calculations

The primary analysis will compare the difference between each treated group separately versus the placebo group (two pair-wise comparisons) in the levels of $\log(Y_{Cp} + 1)$ using an ANCOVA model adjusting for gender, baseline age, and baseline $\log(Y_{Cp} + 1)$. Estimates of the mean and standard deviation of $\log(Y_{Cp} + 1)$ (expressed algebraically as: $\hat{\mu}_{\log(Y_{Cp}+1)}$ and $\hat{\sigma}_{\log(Y_{Cp}+1)}$) in the placebo group were obtained from prior studies. Among patients with baseline C-peptide > 0.2 pmol/ml and \geqq gd2 years, $\hat{\mu}_{\log(Y_{Cp}+1)} = 0.248$ and $\hat{\sigma}_{\log(Y_{Cp}+1)} = 0.179$ (3). An approximation of the mean of Y_{Cp} for the placebo group is calculated by applying the inverse transformation; this yields 0.282 pmo/mL.

Using standard equations for the comparison of two means, a sample size of 38 patients with complete data needed for the primary analysis per group, would provide power of 85% to detect a 60% increase (on the original scale) in the geometric mean C-peptide with either treatment relative to the placebo group using a test at the 0.025 level (one-sided).

Assuming that 10% of the patients will be "lost" (unavailable for the primary analysis), this study will require enrolling 42 eligible patients per group (126 total). The plan is to follow these patients two years from baseline and for up to 2 additional years post-treatment if residual beta-cell function or immunological effects are detected.

TrialNet: GAD Intervention Protocol

The exact final sample size can not be fixed to be exactly because of staggered patient entry. The study will be closed to new patients entering the screening phase when the total number then randomized plus a fraction of those in screening is expected to provide the proper number of eligible patients. Patients who had already conducted the initial screening visit at that time will be allowed to complete screening and be randomized if both consenting and eligible.

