12. STUDY TIMELINE

It is anticipated that patient enrollment will occur during the first two years of the trial. Subjects will be followed until two years after initial treatment. Subjects will be asked to undergo additional follow-up after two years for up to an additional two years with a visit every 6 months. Subjects with undetectable levels of C-peptide on the 30 month or any subsequent visits, will not undergo any further MMTT for assessment of C-peptide.

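### Protocol sections give conflicting rules for follow-up after month 24, and the conditional rule, if applied subject by subject, would select extension data by arm

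*Protocol*

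**What the plan says.** Four places in the protocol describe follow-up after two years.

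- Section 1.1 (Study Duration): "Follow-up for up to 4 years may continue for those who have persistence of beta cell function after 2 years and/or detectable immunologic effects". The sentence goes on to say that these are effects of treatment, judged by descriptive analysis.
- Section 9.4: subjects are followed for two years and then "for up to 2 additional years post-treatment if residual beta-cell function or immunological effects are detected".
- Section 4.9: "Subjects may subsequently be asked to undergo additional follow-up for an additional two years with a visit every 6 months until study end". Visits carry no C-peptide or immunologic condition.
- Section 12: "Subjects will be asked to undergo additional follow-up after two years for up to an additional two years with a visit every 6 months". Again there is no condition.

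The rule for stopping mixed meal tests (MMTTs) also has two forms. Section 4.9 says "Subjects with undetectable levels of C-peptide on the 30 month visit will not undergo any further MMTTs". Section 12 says "Subjects with undetectable levels of C-peptide on the 30 month or any subsequent visits, will not undergo any further MMTT".

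Persistence of beta-cell function and a detectable immunologic effect are given no threshold. Three analyses in section 9.2 have no month-24 limit: the mixed model "of the C-peptide values over the post-treatment period"; the HbA1c, insulin dose and blood glucose means, which use every follow-up value; and the event rates, which divide by total patient-years.

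**The concern.** Sites cannot follow both rules. Who stays in follow-up is a protocol matter, so an analysis plan cannot settle it later.

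The conditional rule also selects on two post-randomisation variables that treatment is meant to change. The immunologic criterion is the more troublesome. Section 6.3 makes it the principal mechanistic aim to "identify measures of immunity to GAD which distinguish between subjects receiving two or three injections of GAD in alum" from those given alum alone. Alum-only subjects have no GAD effect to show, so they would stay mainly because their C-peptide is preserved. GAD-alum subjects could stay for either reason. The retained alum group would then be enriched for good C-peptide even if treatment did nothing.

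At stake are direct between-arm comparisons after month 24 and the open-ended secondary analyses of HbA1c, insulin dose, glucose and event rates. Section 2.1 expects residual function to bring better metabolic control and less hypoglycaemia, so an alum group enriched for it could also look better on those outcomes.

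**Working it through.** **Design effect, as a yardstick (section 9.4).** Placebo mean 0.248 and SD 0.179 on log(Y+1); 60% increase on the original scale; 85% power; one-sided 0.025.

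- Placebo Y = e^0.248 - 1 = 0.2815 (the protocol gives 0.282). Treated Y = 1.6 × 0.2815 = 0.4503.
- Difference = ln(1.4503) - 0.248 = 0.124.
- n = 2 × (1.960 + 1.036)² × 0.179² / 0.1238² = 37.5, so 38 per group, as stated.

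**Assumptions for the illustration (not in the protocol).**

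- Month-24 and later values share the planning mean and SD.
- Persistence means Y of at least 0.2 pmol/mL.
- The immunologic effect is independent of C-peptide within arm and present in 5% of alum and 50% to 90% of GAD-alum subjects.
- The correlation r between month 24 and month 36 is 0.6 to 0.9.

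**Formula.** Let a = (ln 1.2 - mean)/SD and p = 1 - Φ(a), and let q be the proportion with an immunologic effect. The proportion kept is p + q(1 - p). The month-36 mean among those kept is shifted by r × SD × (1 - q)φ(a) / [p + q(1 - p)].

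**No true effect.** a = (0.1823 - 0.248)/0.179 = -0.367, p = 0.643, φ(a) = 0.373.

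| Arm | q | Kept | Of 42 | Shift ÷ r |
|---|---|---|---|---|
| Alum | 0.05 | 0.66 | 28 | 0.096 |
| GAD-alum | 0.5 | 0.82 | 35 | 0.041 |
| GAD-alum | 0.9 | 0.96 | 40 | 0.007 |

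- q = 0.5 in GAD-alum: (0.0406 - 0.0959) × r = -0.033 (r = 0.6) to -0.050 (r = 0.9).
- q = 0.9 in GAD-alum: (0.0069 - 0.0959) × r = -0.053 to -0.080.
- Range: -0.033 to -0.080, which is 27% to 65% of 0.124. A simulation with 1,000,000 subjects per arm gives the same figures.
- With the C-peptide criterion alone, 27 v 27 of 42 are kept and there is no bias.

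**True effect 0.124.**

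- C-peptide criterion alone: 27 v 36 kept; the difference among those retained is 0.073 to 0.090.
- Both criteria: 28 v 39 to 41 kept; the difference is 0.041 to 0.079.

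**Extreme case.** Every GAD-alum subject continues, alum subjects continue only if Y exceeds 0.2, and r = 1. The shift is 0.179 × 0.373/0.643 = 0.104, and 0.104/0.124 = 84%. Cut-offs of 0.1 and 0.3 give 50% and 123%.

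**Mixed model under the same extreme selection, no true effect.** Assumed intercept SD 0.16, slope SD 0.05, residual SD 0.06 and linear decline. The direct month-36 comparison of those retained gives -0.107. A random intercept and slope model using all post-treatment values gives -0.003 (Monte Carlo standard error 0.003). A repeat with the random intercept placed at month 24 gives -0.086 and -0.004 (standard error 0.003).

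**The case against.** The strongest reply is that little of importance rests on data after month 24. The primary outcome is at 12 months, and the named C-peptide secondaries are at 18 and 24 months. The schedule of assessments ends at month 24, and section 6.3 describes the trial as lasting 24 months. No section names a between-arm comparison of those retained later. This stands, and it limits the point to the open-ended secondary analyses and to any direct comparison in the extension.

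The mixed model is also largely protected, as the check shows, when continuation depends on C-peptide values and arm already in the model. That stands with a condition. The model contains no immune variable, and section 6.3 plans to correlate GAD responses with C-peptide, so protection is not assured if selection runs through immune response. The HbA1c, insulin dose, glucose and event-rate analyses adjust for baseline C-peptide but not for C-peptide during follow-up, so they lack that protection.

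A reader might infer bias in the log-rank analysis. The documents do not support this. Its event is the first peak C-peptide below 0.2 pmol/mL, so a subject whose MMTTs stop for undetectable C-peptide has already had the event, and most subjects dropped for lost function will have too. How stopped MMTTs are scored can be left to an analysis plan.

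Finally, section 1.1 says that follow-up may continue and speaks of descriptive analysis, and section 9.4 can be read as a trial-level decision to extend. That reading is possible. The section 1.1 wording nevertheless refers to those subjects who have the feature, and the ambiguity itself needs resolving.

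**Conclusion.** The inconsistency is certain: sections 1.1 and 9.4 set a condition that sections 4.9 and 12 do not, sections 4.9 and 12 differ on the MMTT stop, and the passages must be reconciled.

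The bias is conditional. It arises if the section 1.1 rule is applied subject by subject and the extension data enter a between-arm comparison. Under the stated assumptions a direct C-peptide comparison would be off by about -0.03 to -0.08 on log(Y+1) with no true effect, and a true 0.124 would shrink to 0.041 to 0.079. The effect on HbA1c, insulin dose, glucose and event rates cannot be sized from the protocol.

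A reader might infer that a lasting benefit would be hidden or reversed, or take 84% as the expected size. Neither follows. In the illustrated range a true effect is attenuated but stays positive. The 84% figure needs every GAD-alum subject to continue, no alum subject below the cut-off to continue, and no regression towards the mean. Even then 0.124 - 0.104 = 0.020 remains, and reversal needs the stricter 0.3 cut-off as well. The 12-, 18- and 24-month comparisons and the log-rank analysis are essentially untouched.

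**What to change.** Choose one of two repairs.

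1. State one rule in sections 1.1, 4.9, 9.4 and 12: extension visits are offered to all randomised subjects, whatever their C-peptide or immune response. This removes the selection. The cost is some extra visits, many without an MMTT, for subjects with no residual function.
2. End all between-arm analyses in section 9.2 at month 24, including the mixed model, the means over follow-up and the event rates, and label the extension descriptive. This costs only wording, but gives up between-arm inference after month 24. The four sections must still be brought to one follow-up rule.

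Under either option, give sections 4.9 and 12 the same wording for when MMTTs stop. The sample size does not change, because it rests on the one-year outcome. The change is best made before subjects reach month 24, since those not followed cannot be recovered later.

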2. BACKGROUND AND SIGNIFICANCE

2.1. Rationale for intervention trials to preserve beta cell function in subjects with Type 1 diabetes

The onset of human Type 1 diabetes mellitus is the clinical manifestation of the β -cell failure caused by T cell mediated autoimmune destruction. This results in a life long dependence on daily insulin injections and exposure to both the acute and late complications of Type 1 diabetes mellitus (T1DM). T1DM is a particular burden to children and their families, representing one of the most common chronic childhood diseases. While T1DM can occur into adulthood, there is a bimodal peak age of onset, between ages 4-7 and ages 14-16 years. The world-wide incidence of T1DM is increasing, with the greatest increase in children under the age of 5 years. Despite the significant progress that has been made in its treatment, diabetes mellitus represents a severe burden on the individual and on society as well. Any intervention, which can stop or delay the complete loss of functional residual β -cell mass is significant as it may provide protection against hypoglycemia and provide improved metabolic control resulting in a delay in the micro and macro-vascular complications of diabetes.

Type 1 diabetes mellitus is an immune-mediated disease in which insulin-producing beta cells are completely destroyed resulting in life-long dependence on exogenous insulin. While this beta cell destruction process begins before clinical onset and continues after development of hyperglycemia and diagnosis, at the time of diagnosis subjects retain a significant amount of beta cell function as measured by C-peptide responses to a mixed meal tolerance test. However, this beta cell function deteriorates after diagnosis with the presumed eventuality of absent function over time. As shown in the Diabetes Control and Complications Trial, the persistence of residual beta cell function has been associated with important clinical outcomes, specifically reduction in severe hypoglycemia and complications. In this study, the rate of retinopathy and severe hypoglycemia were reduced by greater than 50% in those with sustained C-peptide when compared with those with undetectable C-peptide (1-3). Additionally, there is growing evidence that residual beta cell function shortly after the diagnosis of diabetes may be much greater than previously thought and may be as much as 50% of subjects without diabetes (4). Thus, an intervention that can enable continued endogenous insulin production would significantly improve the day-to-day management for subjects with diabetes and therefore reduce long-term complications.

2.2. Rationale for the use of GAD-alum

The destruction of the pancreatic beta cells in Type 1 Diabetes (T1D) is associated with cellular immune responses to the pancreatic islet cells, genetic susceptibility involving genes thought to modulate the immune response, and the presence of autoantibodies against several islet beta cell components (i.e., autoantigens). In addition, as these T1D associated autoantibodies often precede the clinical onset of disease, those antibodies directed against glutamic acid decarboxylase (GAD65 ab), IA2 ab, and insulin (IAA) are widely recognized not only as diagnostic markers for autoimmune beta cell destruction but in addition, as predictive markers for the disease (5-6).

Although the involvement of glutamic acid decarboxylase (GAD) in neural transmission is understood by its function as an enzyme converting glutamate to gamma-amino butyric acid (GABA), its specific and unequivocal function in pancreatic beta cells, as well as its role in the pathogenesis of either form of diabetes remains somewhat unclear. Indeed, the reason why GAD is a major autoantigen in autoimmune diabetes is not known. However, despite this lack of understanding, convincing (i.e., reproduced by a broad body of the scientific community) data from the NOD mouse model of type 1 diabetes has shown that an isoform of GAD with molecular mass 65,000 (GAD65) can prevent autoimmune destruction of pancreatic beta cells and subsequent need for exogenous insulin replacement (5-18). These findings indicate the potential of GAD65 administration to provide a preventive treatment for the forms of diabetes involving autoimmunity, most notably those occurring in patients with T1D.

The product is a highly purified and unmodified form of recombinant human glutamic acid decarboxylase (rhGAD65), formulated in aluminum hydroxide. It is an antigen-specific immune modulator that has been shown to slow or prevent autoimmune destruction of pancreatic beta cells by inducing immune "tolerance". In "recent-onset" T1D patients, tolerization is proposed to prevent the destruction of remaining beta cells and thereby maintain residual insulin secretion to minimize the likelihood of acute and long-term diabetic complications as well as improving metabolic control. Available data demonstrate that even relatively modest treatment effects on residual insulin secretion will result in clinically meaningful benefits (1-3).

As described below, pre-clinical and clinical data studies to date suggest that GAD65 in alum immunization is safe, and preliminary data indicates that it may be efficacious in diminishing beta cell autoimmune destruction among subjects with autoimmune diabetes.

3. CLINICAL AND PRE-CLINICAL DATA

3.1. Preclinical Data

3.1.1. Preclinical Safety Data

Two formulations have been evaluated in preclinical and clinical studies. Diamyd[®] bulk biologic substance (formulated in buffer from the manufacturing process) was used for initial preclinical safety studies, a skin Prick Test and a Phase I clinical trial (formulated in PBS). An adjuvant formulation of Diamyd[®] based on Alhydrogel[®] has also been developed for evaluation in Phase II clinical trials (Diamyd[®] Product).

A preclinical safety evaluation program has comprised single and repeat dose toxicity, local tolerance, immunotoxicity and investigation of the potential for effects on behavior, cardiovascular/respiratory and central nervous systems. Evaluation of all preclinical safety studies performed to date have not provided concerns for clinical safety of Diamyd[®] biologic substance (even at multiples of the highest clinically-intended dose level) or Diamyd[®] Product, or identified any target organs of toxicity. Evaluation of the effects of Diamyd[®] in several different animal models of autoimmune diseases did not indicate any potential for undesirable effects on the immune system.

